## C. Innovation

This proposal is innovative in several respects. First, while there is a burgeoning literature on cognitive remediation in schizophrenia (e.g., 65;124-126), most of this work targets higher cognitive processes such as executive functioning and working memory, and assumes that perception is intact. As a result, despite the

[figure not shown]
large body of evidence showing impaired visual perceptual function in schizophrenia, the effects of visual training modules alone are virtually unstudied in this disorder. While CS and PO have been shown to be plastic in terms of performance improvement with repetition in prior laboratory studies, including in people with schizophrenia, the effects of systematic visual training of these processes for longer than a few days have not yet been studied in this population in a controlled study. Second, unlike many cognitive remediation interventions that use games with unclear 'doses' for specific functions, we are targeting two well-understood perceptual processes with interventions that clearly target these processes. Third, UE has been shown to improve CS in non-psychiatric samples, but has never been used in a controlled study of schizophrenia. Fourth, many current perceptual learning approaches emphasize single processing mechanisms and produce results that are specific to the trained stimulus features, which has limited generalizability. The UE program addresses these issues by combining multiple perceptual learning approaches (e.g., engagement of attention, reinforcement) - each of which has been shown in past studies to contribute to increasing the speed, magnitude, and generalizability of improved CS - into an integrated perceptual learning application. UE has been shown to improve not only CS but also functioning in real-world activities (see Section D.1). Fifth, the PO training program we developed (CIT) is innovative (we were able to identify only one published paper on improving PO in any population, and this was over 30 years old). Our proposed intervention is based on knowledge gained from our 30 years of studies in controls and patients about what factors contribute to PO, and how performance can change over time. Despite extensive evidence for PO impairment in schizophrenia, little is known about the maximum extent to which it can be improved, the amount of training needed to obtain gains, the durability of gains, and their functional significance. Sixth, the additive and/or interactive effects of multiple forms of visual remediation have never been investigated. This would be the first examination of whether targeting both CS and PO is more effective than targeting either single process alone. The construct of gain control (operationalized here in the form of CS) and the construct of integration (operationalized as PO) were identified by the NIMH-sponsored CNTRICS initiative, and the RDoC cognitive domain, as high-priority cognitive neuroscience constructs relevant to schizophrenia and its treatment. This study targets both levels. Seventh, we will examine training effects on higher-level processes with a focus on comparing effects on visual vs. non-visual cognition, which has not yet been done in a controlled study.

### D. Approach

#### D.1 Preliminary Data

UE pilot study: Pilot data from patients with schizophrenia at the Nathan Kline Institute (NKI) and Rutgers show good retention with 6 of 7 patients (86%) completing at least 30 sessions. This is similar to previous single-site cognitive remediation studies and to an average retention rate of 87% in a metaanalysis of 40 cognitive remediation studies in schizophrenia. This also matches the 93% retention rate of UE studies in healthy young adults carried out by [name] (co-investigator and developer of UE). Preliminary data show UE is well tolerated, and even enjoyed, as described in our recent publication. Across participants, CS improved 32%, with an increase in the peak contrast spatial frequency of 1 cycle/degree (pre-training peak spatial frequency of  $3.14 \pm 0.24$  vs. post-training of  $4.15 \pm 0.70$ , p=.14, d=0.96). Additionally, patients improved on contour integration (p=.11, d=0.85). With such a small sample (N=6), our results were not statistically significant. However, the magnitude of CS improvement is similar to that from published studies of UE.

UE findings in non-psychiatric samples: In previous research on UE conducted by [name], CS improved in healthy normal-sighted individuals after  $\sim$ 30 sessions of training, with effect sizes ranging from

d=1.6 for LSF to 0.63 for HSF stimuli. In another study, college baseball players displayed significant improvements in CS (Fig. 1) and batting average $^{70}$ after UE training, with effect sizes ranging from d=0.34 to 0.59 (with the lowest effect size for CS to HSF stimuli). Additionally, university students demonstrated improved reading ability after UE training. Specifically, reading acuity improved an average of 13% (d=0.38), moving from a pre-training mean logMAR acuity of -0.06 to a post training value of -0.11, (SD=0.02). Reading speed improved 13% (d=0.57), moving from a pre-training mean value of 240.0 words/minute to a post-training value of 270.6 words/minute  $(SD=8.28)^{21}$ . In addition, older adults with presbyopia

displayed improved CS after undergoing UE training. It is important to note that in the studies of UE in which

CS was assessed, CS improved significantly, as seen in a shift upward across spatial frequencies (see Fig. 1). Effect sizes were relatively large in the trained group in these studies and the average d for LSFs, which is the target for this proposal, ranged from 0.45 to 1.0 across studies. Based on these data and our pilot data in patients described above, we expect UE to lead to significant gains in CS in schizophrenia.

Preliminary and related data that motivate the targeting of CS: In an ongoing study in [name] lab (N=17 thus far), we have found that lower peak CS is related to poorer contour integration (r=.69, p<.01). In a recently completed study in [name] lab (N=32), we found that lower CS at 1 cycle/degree is related to poorer performance on the WAIS PO Index (r=.41, p=.02) and the MATRICS visual learning domain (r=.46, p=.006) in people with schizophrenia. In addition, a cluster analysis showed that people with schizophrenia who were more impaired on CS were also more impaired on speed of processing, PO, visual learning, and emotion recognition (p=0.02 to <0.001), but not on verbal working memory, verbal learning, or symptoms ( $p \ge 1000$ 0.05), suggesting that our visual targets are not manifestations of a generalized deficit. These data fit current models in which CS occurs very early during visual processing, whereas PO is an integrative process that occurs later and involves binding of feature representations (whose guality is determined in part by CS). In addition to effects of low CS on PO, studies have shown that participants with schizophrenia who have impaired CS have greater reading deficits, and poorer facial emotion detection. Further, in pilot work using structural equation modeling (SEM), we have found relationships between abnormal VEPs and impaired visual learning and PO that were significantly mediated by CS. In short, there is reason to expect that improving both CS and PO will lead to higher-level changes in perception and cognition.

## D.2 Inclusion/Exclusion Criteria for R61 and R33

Inclusion: 1) SCID-5 diagnosis of schizophrenia; 2) 18-60 years old; 3) speaks English; 4) able to complete the MATRICS Consensus Cognitive Battery (MCCB) at the baseline assessment (for R33); 5) a raw score of 37 or greater on the Wide Range Achievement Test, Reading subtest (WRAT-3), to establish a minimum reading level (6th grade) and to estimate premorbid IQ; and 6) clinically stable as indicated by no antipsychotic medication changes in the last month or if on depot, no change in the past 2 months. Exclusion: 1) history of intellectual disability, or developmental or neurological disorder; 2) history of brain trauma associated with loss of consciousness for > 10 minutes or behavioral sequelae; 3) alcohol or substance use disorder within the last 6 months; and 4) history of eye disease (e.g., glaucoma, retinopathy). Effects of tobacco use and medication dose equivalents, including an index of anticholinergic load, will be explored in data analyses.

# D.3 R61 Phase

Aims: (i) To evaluate the effects of UE and CIT on the CS and PO targets, respectively; (ii) to determine if the criterion for continuing to the R33 phase is met; and (iii) if the criterion is met, to determine the most effective intervention condition and optimal duration of treatment, to inform the R33 study design.

Study design: 80 subjects will be enrolled in this study: 20 per arm. 40 will be recruited at each site (Rutgers and NKI). The intervention will continue for 40 sessions, with targets assessed before training, after every 10 sessions, and at 6 months post-training for a total of 6 visual assessments. With 3 sessions per week, the intervention will take between 13-14 weeks. Each site will enroll ~ 2 participants/month, beginning after the first half of Y1, which is similar to what Keefe et al. estimated as a "reasonable rate of recruitment for a largescale efficacy trial" of cognitive remediation. Because, at the 6-month follow-up, nearly all patients are expected to still be in the partial hospital program, or an outpatient program (at Rutgers), or on inpatient units at the Rockland Psychiatric Center (RPC) or NKI, we expect attrition to be minimal. However, several methods, including monthly phone calls (see Recruitment and Study Timeline), will be used to maximize retention. For the R61 and R33, training sessions will be run in small groups by front-line staff who have already received training in these interventions, or whom we will train, with no more than a 3:1 participant:staff ratio. Randomization: Subjects will be randomly assigned, within site, to one of the 4 conditions (UE&ACCT, CIT&ACCT, UE&CIT and ACCT&ACCT) in a ratio of 1:1:1:1. The treatment assignment will be made after a subject has met all entry criteria and completed baseline testing, to avoid bias.

Milestones (Go/No-Go Criterion): We will proceed to the R33 phase if: 1) the UE-related effect size (i.e., the effect size of the difference between the UE&ACCT (or UE&CIT) and ACCT&ACCT groups in the degree of change in CS) is greater than or equal to Cohen's d=0.4 for **either** the psychophysical **or** ssVEP CS task: and/or 2) the CIT-related effect size (i.e., the effect size of the difference between CIT&ACCT (or UE&CIT) and ACCT&ACCT groups in the change on **either** of the PO tasks) is greater than or equal to d=0.4. Pre-post change scores for CS and PO target assessments will be calculated for each individual and used to determine effect sizes between groups. We will not control for baseline values consistent with recommendations to use "straight" change scores when examining cognitive change across two time points.

Rationale for our effect size choice: The effect size criterion we have chosen for the R61 "go" signal (d=0.4)

is similar to that observed in many studies of cognitive remediation, and of other treatments for this population, such as skills training and family psycho-education. However, less is known about effect sizes of perceptual remediation, and most of the evidence on this in schizophrenia comes from studies of auditory remediation using the Posit Science auditory training module, which includes training on both low-level auditory targets and higher-level auditory-verbal cognition (e.g., verbal working memory and learning). Results from one study indicated an improvement in the target of auditory-processing speed that was of large effect (d=0.875). The authors also observed a medium-large effect on global cognition (d=0.73). Results from other studies of this auditory training module in schizophrenia have indicated large treatment effects (d=0.86) for both verbal learning and global cognition, and a medium effect (d=~0.65) on the auditory target of P50 gating. While these effect sizes are larger than our chosen criterion (d=.4), it is also important to note that some studies of Posit Science modules have not demonstrated significant improvement on non-trained tasks. Moreover, across studies, the largest effects have tended to come from studies where daily training (5 days a week) was used, and subjects were paid for completing training sessions, and these are two conditions that can rarely be met in real world psychiatric clinics. These considerations have informed our choice of the 'go signal' criterion (i.e., d=.4), because there are as of yet very few published studies of visual remediation in schizophrenia. One small (N=9) uncontrolled study of visual backward masking training found an effect size of d=.43 for improvement in the MATRICS domain of Visual Learning. Within our group, [name] observed an improvement in contour integration performance among participants with schizophrenia after 4 consecutive days of practice on a contour integration task (phi=0.63, which corresponds to a large effect). Even larger effect sizes were seen for changes in CS (d=0.96), and PO (d=0.85) in our small pilot sample of patients with schizophrenia (Section D1), but given the small sample size and lack of a control group in that study it can be assumed that the real effect size is lower. Thus, findings from these initial evaluations of visual remediation support our use of d=0.4 as a conservative level of change on the outcome measures and as a "go" signal for target engagement. However, we acknowledge that it is not yet clear from the literature how an effect of this size relates to meaningful improvements in visual and higher-order cognitive processing, and/or functional capacity. The proposed R33 will allow us to address this guestion in a preliminary manner. If results from this trial are positive, we will seek funding for a larger trial to evaluate the impact of this treatment on functional outcomes, and to identify mediators/moderators of treatment response. If the Go criterion is met for any of the treatment conditions, we will perform a thorough investigation of the effects of UE, CIT, and UE&CIT on the CS and PO target scores to determine which remediation strategy to use for the R33. Analyses will also include (i) assessment of the trajectory of performance on the target measures over the course of treatment; (ii) determinations of whether the improvements plateau prior to the 40th session or whether they continue throughout the training period; and (iii) evaluations of whether any combined effects of UE and CIT are additive or multiplicative. These goals will be accomplished by first graphically examining the trajectories of target change to assess whether they are linear, monotonic non-linear, guadratic, or any other shape. After that, appropriate models for longitudinal data analysis will be applied to estimate improvement rate and time to asymptote. We will account for CPZ-equivalent dose of antipsychotic medications in all models, using CPZ dose as a time-varying covariate if necessary, and will also account for type of antipsychotic medication and anticholinergic load. Those models will also be used to examine whether baseline characteristics moderate the effect of UE and/or CIT on the targets. These analyses will allow us to ascertain: 1) whether UE alone, by targeting CS function, has a cascading effect on PO; 2) whether CIT improves CS while targeting PO function; and 3) whether UE&CIT has a stronger effect than either intervention alone for any outcome. Based on these results, the optimal intervention will be determined based on it having a significantly larger effect size for at least one target. If all 3 treatment conditions are effective to an equivalent degree, the criterion will be reaching asymptotic level of improvement earliest.

[figure not shown]

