# **D.6.b Visual Targets**

Contrast Sensitivity: CS functions will be obtained by presenting 5 horizontal sine-wave gratings at the following SFs: 0.5, 1, 4, 7, and 21 cycles per degree. Spatial frequency is the number of pairs or cycles of light and dark bars in 1 degree of visual angle, expressed as cycles/degree, with fewer pairs corresponding to lower SF. Each grating will be presented for 32 milliseconds. An up-and-down transformed response method will be used to obtain contrast thresholds with a criterion of 70.7% correct responses for each SF. The mean of 10 reversals will be used to obtain thresholds. Presentation of the different SF gratings will be interleaved in a random order. A spatial 2-alternative forced-choice procedure will be used. Gratings will be presented on either the right or left side of the screen, and the participant's task is to determine on which side the gratings appeared. Results will be plotted as CS (which is the reciprocal of threshold) vs. SF. Increased CS indicates better performance. Participants will be tested binocularly after being light-adapted to the background luminance of the display for 15 minutes. Test re-test reliability of this measure in a group of 15 controls and 31 patients (tested at the [name] lab at NKI) was an ICC of .76 at 0.5 cpd and .67 and 1 cpd. The test-retest reliability is weaker at the peak SF of 4 cpd (.25) and improves with higher SFs (ICC=.69 for 7 cpd and .57 for 21 cpd). The target variable is the average CS for the two LSFs (0.5 cpd and 1 cpd). We expect to see more of an effect of the remediation on LSF, but we will also assess CS at the other SFs, and specifically compare LSF

results to results at 7 cpd, which also has high reliability, to determine if effects are LSF-specific. VEP Contrast Responses: This VEP technique was developed by [name] and colleagues and has been used in studies of schizophrenia , autism^82, and glaucoma detection. The response measures are quickly and easily obtained, requiring no behavioral response from the participant. Parameters to be used have been optimized in our studies of schizophrenia. Steady-state VEPs are elicited to checkerboard patterns that are luminance-modulated sinusoidally (~12 Hz) with contrast increases in 7 discrete octave steps. Each

ure 4: VEP Contrast stimuli examples				
4%	8%	16%	32%	64%

[figure not shown]

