step is ~1.6 sec in duration to yield an entire contrastresponse function in less than 10 seconds (Fig. 4). The initial step has 0% depth of modulation (DOM) and this is followed by steps of 1, 2, 4, 8, 16, and 32% DOM. The set of steps is presented 10 times. In the contrast response function, as the DOM rises, the signal-to-noise ratio (SNR) increases from below a value of 1 to a value

greater than 1. To obtain the contrast at which SNR=1 (i.e., the contrast threshold), linear interpolation will be done for the first two consecutive contrasts (DOMs) at which SNR is less than one and then greater than one

. Test-retest reliability of low-contrast VEP responses in schizophrenia (N=32) is good (ICC=0.70; [name] lab, unpublished data). In addition, the 95% confidence regions for the 10 runs per person show good reliability within an individual. [name] has observed a within-subjects correlation of r=.41, (p<0.001; N=74) between indices from these VEP and psychophysical CS assessments.

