Jittered Orientation Visual Integration (JOVI) Task: Stimuli consist of oval contours, made up of 18 Gabor elements separated by 1° of visual angle, that either point left or right (Fig. 3). The contours are embedded in 298 distractor Gabors. Difficulty is manipulated by increasing the degree of orientational jitter of the Gabors making up the contour. Jitter levels will be 7°, 9°, 11°, 13°, and 15°, as in recent studies. Trials will be blocked according to the amount of orientational jitter, with 12 trials per block. Blocks will be presented in increasing order of difficulty, with each block presented 4 times for a total of 240 trials (4 repetitions x 5 blocks x 12 trials). In addition, each block will contain 4 catch trials in which a contour with no orientational itter is presented without background elements, or is presented with background elements but with a line drawn along the contour. These trials are included to identify subjects who respond randomly or who are not paying adequate attention to the task. As in past studies, only subjects who obtain 75% or higher accuracy on these trials will be included in data analyses. Each stimulus is shown for 2 seconds, followed by a 1 second inter-stimulus interval. The participant presses a right or left arrow key to indicate the direction of the contour. There will be practice trials prior to the task, using the format in past studies. This task was optimized for use with participants with schizophrenia in a previous 5-site study, which found good test-retest reliability. The dependent variable is number correct, corrected for guessing (to equate with subjects who respond when unsure of the correct answer, who will be right 50% of the time).

Ebbinghaus Illusion Task. On each experimental trial, subjects are shown two target circles—one on the left of the screen and one on the right, and their task is to indicate which is larger. On half the trials, these

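### The R61 go/no-go effect size is not adjusted for baseline or site; a four-arm ANCOVA would usually sharpen it a little, using data already held

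*Combined protocol and SAP*

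**What the plan says.** Under Milestones, D.3 defines the go/no-go effect sizes: "Pre-post change scores for CS and PO target assessments will be calculated for each individual and used to determine effect sizes between groups". It then says "We will not control for baseline values", citing recommendations for plain change scores over two time points. A go needs d of at least 0.4 on any one of eight contrasts: UE or UE&CIT against ACCT on two CS tasks, and CIT or UE&CIT against ACCT on two PO tasks. No test is attached, and the SD in the denominator of d is not specified.

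D.3 also says "Subjects will be randomly assigned, within site, to one of the 4 conditions", with assignment made after baseline testing and 20 patients per arm. The later R61 longitudinal models adjust for medication variables. The R33 H1 model in D.4 uses target values at every time point. Neither names site, although the R33 is also randomised within site.

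**The concern.** The go decision compares noisy point estimates from arms of 20 with a sharp cut at 0.4. In a randomised comparison, a change score fixes the baseline slope at 1. When the pre-post correlation is below 1 and the spread is stable, that over-corrects, and chance baseline imbalance leaks into d. All eight contrasts share one control arm, so an unlucky control baseline on a target moves both of its contrasts the same way. ANCOVA estimates the slope instead and needs no new data. What is at stake is a somewhat noisier gate, not a biased one.

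**Working it through.** **The plan's own precision figure.** D.3 (Sample size determination) gives a 95% CI of .02 to .91 for d=0.4. For two groups of 20, SE = √(2/20 + 0.4²/(4×20)) = √0.102 = 0.319, so the CI is 0.4 ± 0.626, or -0.23 to 1.03. The stated interval is not reproduced; it rests on pilot data that the documents do not give. Applying the VEP ratio below, SE = √(0.102×0.862) = 0.297 and the CI is -0.18 to 0.98. Baseline adjustment does not rescue that statement, which is a separate matter.

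**Inputs (D.6.b), used as stand-ins for the pre-post correlation ρ.**
- CS: "The target variable is the average CS for the two LSFs (0.5 cpd and 1 cpd"), with "ICC of .76 at 0.5 cpd and .67 and 1 cpd".
- VEP: "Test-retest reliability of low-contrast VEP responses in schizophrenia (N=32) is good (ICC=0.70"). This is for low-contrast responses, while the described outcome is an SNR=1 threshold, so it is approximate.
- JOVI: "which found good test-retest reliability", without a figure. Ebbinghaus: none. Assumed ρ of .5, .7 and .9.

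**Reliability of the CS average.** Let c be the correlation between the two frequencies (assumed .3 to .7, equal variances, uncorrelated errors). Reliability = (.76+.67+2c)/(2+2c). At c=.3 this is 2.03/2.6 = .781; at c=.7 it is 2.83/3.4 = .832.

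**Variance ratio, ANCOVA to change score, equal pre and post SDs.** Ratio = (1+ρ)/2 × slope penalty. The penalty is 1+1/(df-2), where df is what remains for the baseline slope after arms and site. Four arms: 80-5 = 75, penalty 1+1/73. Two arms: 40-3 = 37, penalty 1+1/35.

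| Target | ρ | Four-arm ratio | 20 per arm acts like |
|---|---|---|---|
| CS | .781 to .832 | 0.903 to 0.929 | 22.2 to 21.5 |
| VEP | .70 | 0.862 | 23.2 |
| PO (assumed) | .5 | 0.760 | 26.3 |
| PO (assumed) | .7 | 0.862 | 23.2 |
| PO (assumed) | .9 | 0.963 | 20.8 |

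Break-even is ρ = 2/(1+1/73)-1 = .973 with four arms and 2/(1+1/35)-1 = .944 with two. These values hold only with equal SDs.

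**Unequal SDs.** With k = SD post/SD pre, ratio = (1-ρ²)k²/(1+k²-2ρk), times the penalty. At k = 1/ρ the first factor is exactly 1. For ρ=.8, k=1.25: 0.36×1.5625/(1+1.5625-2) = 0.5625/0.5625 = 1. ANCOVA then costs only the penalty, 1/73 = 1.4% (four arms) or 1/35 = 2.9% (two arms). If the spread narrows, the gain grows: ρ=.8, k=0.8 gives 0.2304/0.36 = 0.64 before the penalty.

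**One contrast, no true effect.** P(d ≥ 0.4) with change scores = P(Z > 0.4/√0.1) = P(Z > 1.265) = 10.3%. With four-arm ANCOVA on the same scale, divide 0.4 by √(0.1×ratio): CS 9.2-9.5%, VEP 8.7%, PO at ρ=.5 7.3%. At a true d of 0.4 the estimate is centred on the cut, so about 50% pass under either method.

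**Any of eight contrasts, by simulation.** There were 10,000 trials per setting, 20 per arm, normal scores, equal SDs, and no site effect or missing data. The CS-VEP correlation was taken from D.6.b ("within-subjects correlation of r=.41"); other between-outcome correlations were assumed 0 or .4.
- No true effect: P(go) 45.0-54.9% with change scores, 39.1-51.4% with four-arm ANCOVA. The fall is about 2-8 points, depending on the setting.
- True d=0.4 on all eight: 94.4-98.9% against 94.3-98.9%.
- True d=0.4 for CS under UE only (6,000 trials per setting, two-arm ANCOVA without site, ρ .8 for CS and .7 for VEP, other correlations 0): 74.1% to 71.6% with PO ρ .7, and 73.7% to 69.8% with PO ρ .5. At other correlations of .4 the fall is about 1-2 points. With the effect on JOVI under CIT only, it is about 2-3 points.

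**Scale of d.** The ANCOVA residual SD is √((1+ρ)/2) times the SD of change. Dividing by it at ρ=.70 inflates d by 1/√0.85 = 1.085. That cancels the fall in false passes and lowers the real bar, so the denominator must be fixed in advance.

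**The case against.** The choice is deliberate, pre-specified and referenced, and the estimator is valid. That stands: this is an efficiency preference, not an error. The references cannot be examined here. As worded, the rationale concerns measuring change over two time points and does not address the precision of a comparison between randomised arms.

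A reader might infer that the go decision ignores baseline or is biased. The documents do not support this. Baseline enters by subtraction, and assignment is random and follows baseline testing.

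A reader might also infer that ANCOVA wins at any correlation below .94 or .97. That needs equal SDs, and training could widen the spread. D.1 reports a 32% CS improvement in the pilot; if proportional, k is about 1.3, close to 1/ρ. The spread of peak spatial frequency there went from 0.24 to 0.70, though with N=6 and on a measure that is not the target. So the sign of the net gain for CS is uncertain, but the possible loss is small.

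Nor is the chance of a true go unchanged in every case. When only one contrast carries an effect, overall P(go) drops, and the and/or hypotheses in section B make partial effects an expected case. The drop comes from fewer spurious passes on the other contrasts.

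Finally, the gain is small beside the any-of-eight rule, and section B relies on R33 replication against spurious findings. Both stand. Section B and D.3 also plan to examine how improvement depends on baseline, but that does not enter the go/no-go d.

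**Conclusion.** The point holds as a modest, usually favourable gain in precision with a bounded cost. The variance reductions of about 7-10% for CS and 14% for VEP assume that reliability stands in for the pre-post correlation and that SDs are equal. The CS reliabilities pool 15 controls with 31 patients, which may overstate the correlation in a patient-only trial and so understate the gain. The PO range (4-24%) rests wholly on assumed correlations. No gain from site can be computed, because no site variance is given; the case for including it is the stratified randomisation.

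The change lowers the false-go rate somewhat but leaves it at about 39-51% in these settings, so it does not cure the multiplicity of the rule. Minor priority, moderate confidence.

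**What to change.** **D.3, Milestones.** For each target, fit one ANCOVA across the four arms: the post-training score (the same value the change score would use) on arm, baseline score and site. Take each go contrast from that model and divide the adjusted difference by the pooled SD of change, stated in advance, so that 0.4 keeps its scale. Report the unadjusted change-score d as a sensitivity analysis.

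**D.4, H1.** Add site to the mixed model as the randomisation stratum. Baseline needs no extra term there, since the model already uses the values at each time point.

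**Cost.** A few sentences of analysis wording, a few degrees of freedom, and an assumed common baseline slope across arms. No extra patients, visits or measurements are needed.
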